Primary Objective:	Compare 2 extemporaneously prepared AC suspensions at 2 doses (4 combinations in		
	total) in healthy volunteers for palatability/tolerability		
Patient Population:	Healthy adult volunteers		
Inclusion Criteria:	Age >18 years		
	No use of prescription medications, including oral birth control, currently or in the last		
	30 days		
	Sexually active women must be using an effective form of contraception.		
Exclusion Criteria: • At risk of GI hemorrhage or perforation due to underlying pathology, recen			
	or medical conditions that could be adversely affected by the administration of AC.		
	Planning to have an endoscopic procedure		
	Known hypersensitivity to AC		
	Non-English speakers		
Study Plan:	In the proposed pilot study, we will compare 2 extemporaneously prepared AC		
	suspensions at 2 doses (4 combinations in total) in healthy volunteers for		
	palatability/tolerability.		
Study Product	Medical Grade Activated Charcoal		
Enrollment Plan:	12 healthy adults enrolled in a 4 month period		

Protocol Schema

12 healthy volunteers
Daily AC
4 possible solution-doses
Daily experience rating

Figure 1: Study schema. We will determine the most favored 2 combinations (solution-doses) from 4 possible options in 12 healthy volunteers.

1 Objectives

1.1 Primary Objective

The primary objective is to compare 2 extemporaneously prepared Medical Grade Activated Charcoal, "AC" suspensions at 2 doses (4 combinations in total) in healthy volunteers for palatability/tolerability.

1.2 Secondary Objective

Determine the incidence of grade 2 and above SAEs deemed at least probably related to AC.

2 Background and Rationale

2.1 Infectious Complications in Chemotherapy

Antibiotics disrupt gut microbial communities (dysbiosis). A large fraction of most antibiotics, even when administered intravenously, reaches the colonic lumen and its commensal flora. Antibiotics can reach the gut lumen via mechanisms that include incomplete absorption in the small bowel (e.g., macrolides)¹, hepatic excretion via bile (e.g., tetracyclines)², or active transfer across the intestinal mucosa into the gut lumen (e.g., fluoroquinolones)³.

In the absence of antibiotics, a stable and diverse gut microbiota effectively inhibits colonization by potential pathogens. In the presence of antibiotics, however, pathogenic organisms can grow and cause intestinal and systemic infections. The best example for such infections is *C. difficile* infection (CDI). Even a single dose of an antibiotic (e.g. pre-operative single-dose intravenous antibiotic) can lead to CDI. Surprisingly, no attempts have been made to prevent dysbiosis in individuals exposed to antibiotics. A novel strategy that protects the indigenous microbiota without detracting from the beneficial effects of antibiotics could prevent pathobiont outgrowth and reduce infectious complications of antibiotic use.

2.2 Prevention of Dysbiosis

It is important to discover ways to prevent the untoward consequences of dysbiosis in individuals exposed to antibiotics. The use of oral AC, a potent non-absorbable adsorbent, may protect the gut microbiota by adsorbing the fraction of intravenous (IV) antibiotics that ultimately reaches the intestinal lumen.

2.3 Activated Charcoal

Activated charcoal (AC) is a processed form of carbon with small, low-volume pores that increase the surface area available for adsorption. As a potent adsorbent with no systemic absorption from the gut, AC is a standard and effective agent used in the management of poisonings when gastrointestinal decontamination of drugs or chemicals is indicated.

2.4 Rationale

Investigators are looking for new ways to protect the microbiome during the period of antibiotic exposure, improve the safety of antibiotics and reduce the rate of dysbiosis-related complications in patients. Determining the palatability and tolerability of AC in healthy volunteers in this research will aid in the design of future trials to investigate the efficacy of AC in patients.

3 Study Design

We will use the powder form of medical grade oral AC and mix it with liquids for administration. 12 healthy volunteers will be enrolled to determine the two most palatable and tolerable AC combinations. There will be a total of 4 combinations (2 AC doses and 2 solutions) in stage 1. Each participant will drink an assigned combination every day for 3 consecutive days (Monday, Tuesday, Wednesday, "M/T/W") and switch to a different assigned combination M/T/W the following week. AC solution assignments will be defined before the study using a balanced incomplete block design. Each subject will rate their experience using a 5-point scale every day for the 12 days they are on study.

The following outcome variables will be measured:

- (i) Each healthy volunteer will rate their experience using a 5-point scale (1=terrible, 2=bad, 3=okay, 4=good, 5=great) every day.
- (ii) To evaluate tolerability, after each round of study product consumption, a member of the study team will contact the subject and screen for grade 2 or higher AEs and SAEs

4 Participant Selection

Study entry is open to adult volunteers regardless of gender or ethnic background. While there will be every effort to seek out and include women and minorities, the subject population is expected to reflect the population of Minnesota.

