6.2 Subject Monitoring

Healthy volunteers will be observed for fifteen minutes after consuming the AC. Upon leaving the research unit, they will have access to the CRA via phone. For 2 days after each round of study product consumption, a member of the study team will contact the subject and screen for all grade 2 or higher AEs and SAEs.

Subjects with an adverse event will be followed until the event has resolved or stabilized with sequelae.

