6.3 Management of Selected Expected Toxicities

Toxicity data is based on studies using pharmaceutical grade AC for treatment of intentional overdose/poison control. These doses are much higher than the planned doses of medical grade AC on this protocol. Lower doses are thought to be more tolerable.

- The most common toxicity of AC (doses used for poisoning treatment) is nausea/vomiting, ranging from 15-27%.
- Pulmonary aspiration is the most serious complication, occurring in <1% of patients. AC will not be administered to patients at risk for aspiration.

It should be noted that the cause of aspiration is multifactorial, and part of the risk reported in studies should be contributed to the effect of toxin or the loss of protective reflexes in cases of poisoning. We do not expect these to be present in our participants.

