8.1.7 Toxicities

GI Effects

May cause vomiting, constipation, diarrhea, and GI obstruction or fecal impaction in dehydrated patients.

Generally should not be used when decreased peristalsis present (reduced or absent bowel sounds); if risk of GI obstruction, perforation, or hemorrhage exists; if surgery has occurred recently; or if electrolyte imbalance or volume depletion exists.

Pulmonary Effects

Aspiration of activated charcoal may lead to more severe complications than aspiration of gastric contents alone. Aspiration from vomiting or misdirected nasogastric catheter has resulted in granulomatous reactions, bronchiolitis obliterans, tissue reaction to suspension agents (sorbitol, povidone), increased lung permeability, and rarely, death.

Use of Fixed Combination

When used in fixed combination with other agents, consider the cautions, precautions, and contraindications associated with the concomitant agents.

Common Adverse Effects

Vomiting, diarrhea, constipation, black stools.

9 Event Monitoring, Documentation and Reporting

Toxicity and adverse events will be classified and graded according to NCI's Common Terminology Criteria for Adverse Events version 5.0 (CTCAE V5) and reported on the schedule

below. A copy of the CTCAE can be downloaded from the CTEP home page. (http://ctep.cancer.gov/protocolDevelopment/electronic applications/ctc.htm#ctc 50).

The following definitions of adverse events (AEs) and serious adverse events (SAEs) will determine whether the event requires expedited reporting via the SAE Report Form in addition to routine documentation in the OnCore AE case report form (CRF).

Note: throughout this section the generic term "study drug" refers to study product, medical grade Oral AC.

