9.2 Event Documentation

Participants will be monitored for adverse events from the 1st dose of study treatment through day 12. After that time point, events meeting the definition of serious and at least possibly related to study treatment will be documented upon knowledge.

We will collect the following Grade 2-5 adverse events attributable to AC:

Aspiration of activated charcoal

In addition any event meeting the definition of a serious adverse event (SAE) regardless of attribution that occurs during this period will be documented in the source document and recorded in OnCore.

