11.2 Secondary Endpoint

Safety, defined by the incidence of grade 2 and above AEs deemed at least probably related to AC by day 12.

12 Statistical Considerations

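### Section 3(ii) evaluates tolerability by a grade 2+ adverse event screen, so the mild GI effects the protocol expects are captured only indirectly, in a global rating and a form item that no analysis uses

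*Combined protocol and SAP*

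**What the plan says.** The primary objective (Section 1.1) compares four solution-dose combinations for palatability and tolerability together. Section 3 then names two outcome variables: (i) a daily 1-5 experience rating, and (ii) for tolerability, a contact after each round in which staff "will contact the subject and screen for grade 2 or higher AEs and SAEs".

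The grade 2 floor recurs:

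- Section 6.2 has staff "screen for all grade 2 or higher AEs and SAEs" for two days after each round.
- Section 11.2 defines the secondary endpoint, labelled safety, as the "incidence of grade 2 and above AEs deemed at least probably related to AC by day 12".
- Section 9.2 opens its list with "We will collect the following Grade 2-5 adverse events attributable to AC" and names one item, aspiration of charcoal. Serious events are documented in addition.

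On expected effects, Section 6.3 gives nausea/vomiting at 15-27% under poisoning doses and adds: "Lower doses are thought to be more tolerable". Section 8.1.7 lists the common effects as "Vomiting, diarrhea, constipation, black stools".

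Two other sources bear on tolerability. Section 12.3 selects the most tolerable/palatable combination by highest mean rating, supported by the percentage of ratings of 1 or 2. Item 2 of the rating form (Appendix II) asks about any issue since the last drink that the volunteer thinks may be charcoal-related, with no severity threshold.

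**The concern.** The effects that the protocol itself expects are gastrointestinal, and it expects them to be milder at its lower doses. In healthy volunteers, grade 1 nausea or bowel change is a plausible way for four drinks to differ in tolerability. The outcome that Section 3 assigns to tolerability starts one grade above that.

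Section 9.2 is narrower still. Read literally, non-serious grade 2 vomiting would fall within the Section 6.2 screen and, if judged at least probably related, the Section 11.2 endpoint. It is nevertheless not on the collection list.

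At stake is what the pilot can hand to the later patient trials that Section 2.4 mentions. It would report a mean rating that mixes taste and symptoms, and a grade 2+ count that may be empty. An empty count from six volunteers says little about tolerability.

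**Working it through.** **1. Replication.** Section 12.1 states six volunteers per combination. From Table 1: 12 volunteers × 2 rounds ÷ 4 combinations = 6, with three in each week. The figure is reproduced. There is no alpha, power or effect size to check; Section 12.3 plans no hypothesis tests.

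**2. Where a grade 1 GI symptom could appear.**

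| Source | Can it hold a grade 1 symptom? | Is it used in an endpoint or analysis? |
|---|---|---|
| Post-round contact (3(ii), 6.2) | No, starts at grade 2 | Feeds 11.2 |
| Collection list (9.2) | No, Grade 2-5 aspiration only, plus serious events | Feeds 11.2 |
| M/T/W AE screen (Section 7) | No grade stated in the schedule; 9.2 does not list such events | None stated for grade 1 |
| 1-5 rating (6.1.3, Appendix II item 1) | Only as part of one overall score | Yes: 11.1 and 12.3 |
| Form item 2 (Appendix II) | Yes, ungraded | No |

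**3. Form timing.** Sections 3 and 6.1.3 have ratings every day to day 12. The Section 7 schedule has them on M/T/W only. Under the schedule, no form follows the final Wednesday of week 2. Late week 1 effects could reach a form only on the next Monday, after the new combination has been drunk (6.1.3 places the rating after drinking). The Th/F contacts would then be the only planned check after each round's last dose, and 6.2 sets them at grade 2+.

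**4. How sparse a grade 2+ tally would be.** Let p be the chance that a volunteer has a counted event on one combination. Then P(0 of 6) = (1 − p)^6, and the expected number of combinations with no event is 4(1 − p)^6. The last column treats combinations as independent, an approximation because each volunteer takes two. The documents give no p, so a range is shown.

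| p | P(0 of 6) | Expected zero combinations of 4 | P(at least 3 of 4 zero) |
|---|---|---|---|
| 1% | 0.94 | 3.8 | 0.98 |
| 2% | 0.89 | 3.5 | 0.93 |
| 5% | 0.74 | 2.9 | 0.71 |
| 10% | 0.53 | 2.1 | 0.36 |
| 15% | 0.38 | 1.5 | 0.15 |
| 27% | 0.15 | 0.6 | 0.01 |

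P(0 of 6) equals 0.5 at p = 1 − 0.5^(1/6) = 0.109, about 11%.

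**5. Link to the one rate in the documents.** The 15-27% in Section 6.3 is for poisoning doses, with no grade stated. Assume, for illustration, that 10-50% of such events reach grade 2. Then p runs from 0.15 × 0.10 = 1.5% to 0.27 × 0.50 = 13.5%, P(0 of 6) from 0.91 to 0.42, and expected zero combinations from 3.7 to 1.7. Section 11.2's relatedness filter could only lower p.

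**6. What an empty cell shows.** The one-sided 95% upper bound for 0 of 6 is 1 − 0.05^(1/6) = 0.393, or 39%.

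**7. What any-grade counting would give.** At 15-27%, the expected number affected per combination is 6 × 0.15 = 0.9 to 6 × 0.27 = 1.6. Even a true difference of 15% against 27% is 6 × 0.12 = 0.7 of a volunteer.

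**The case against.** A reader might infer something stronger: that tolerability is measured only by grade 2+ events, that mild effects go unrecorded, and that the comparison of combinations will be mostly zeros. The documents do not support this.

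- Section 12.3 picks the most tolerable/palatable combination on the mean 1-5 rating. The form asks about the day's charcoal experience, not taste alone, so a volunteer with mild nausea can score lower. Those scores cannot be zeros.
- Form item 2 can record mild issues.
- The Section 7 rows for AE screening state no grade floor.
- No comparison of AE counts between combinations is planned, and Section 11.2 calls its count safety. Nothing in the plan says that a tolerability claim will rest on that count.
- Mostly zeros depends on an assumed grade 2 share. At the upper end of the illustration P(0 of 6) is only 0.42.

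All of this stands. So does the remark that any-grade counts of about one volunteer per combination cannot rank four combinations.

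What remains is narrower. Section 3(ii) ties tolerability to the grade 2+ screen, Section 11.1 calls the rating one of palatability, and a single overall score cannot show whether a drink tasted bad or caused symptoms. Item 2 could show this, but no analysis uses it.

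**Conclusion.** The point holds as a gap in how tolerability is captured and reported, not as a failure of the primary ranking. Every stated grade threshold for AE screening, collection and the safety endpoint begins at grade 2. The expected mild GI effects reach the data only through a global rating and an unanalysed form item.

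The size is conditional. A grade 2+ tally by combination would be mostly zeros if the true rate is below about 11%, and would not be at 15-27%. The documents do not say which applies, and their expectation of better tolerability at lower doses gives a direction but no rate. Whatever the rate, zero of six is compatible with a true rate up to 39%, so an empty grade 2+ table would be weak evidence of good tolerability. The calculation assumes independent volunteers with a common rate within a combination.

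**What to change.** In Sections 3(ii), 6.2 and 9.2, record nausea, vomiting, diarrhea and constipation of any grade at the existing M/T/W screens and Th/F calls, with the day of onset so that each is assigned to the right round. Code the answers to form item 2 to the same terms. In Section 12.3, add a table of any-grade incidence by combination (volunteers affected out of volunteers treated) as a descriptive tolerability outcome beside the rating. Leave the grade 2+ count in Section 11.2 as the safety endpoint, and align the Section 9.2 list with it.

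Reconcile the rating-form timing: daily to day 12 in Sections 3 and 6.1.3, against M/T/W in the Section 7 schedule.

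The cost is a few lines on the existing AE case report form, more minor entries, and some coding of item 2. No visits or calls are added. With six volunteers per combination, the table would show which symptoms accompany a low rating, but it should not be used alone to rank the combinations.

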4.1 Inclusion Criteria

- Age ≥18 years
- No use of prescription medications, including oral birth control, currently or in the last
 30 days
- Sexually active women must be using an effective form of contraception. Note that subjects who are on oral contraception should use an additional form of contraception such as barrier methods, as AC may interfere with the efficacy of oral contraceptive.

 Voluntary written consent signed before performance of any study-related procedure

4.2 Exclusion Criteria

- At risk of GI hemorrhage or perforation due to underlying pathology, recent surgery, or medical conditions that could be adversely affected by the administration of AC.
- Planning to have an endoscopic procedure
- Known hypersensitivity to AC
- Non-English speakers

5 Patient Registration

Registration will occur after the participant has signed the subject consent and eligibility is confirmed, but before any study procedures have occurred. To be eligible for registration to this study, the participant must meet each criteria listed on the eligibility checklist (found in appendix I) based on the eligibility assessment documented in the participant's research record.

5.1 Participant Identification

Healthy Volunteers will respond to poster advertisements containing a brief study description and the contact information of the study coordinator.

5.2 Study Enrollment and Dose Level Assignment

Upon completion of the screening evaluation, eligibility confirmation and obtaining written consent the Study Coordinator or designee will enroll the volunteer on study in OnCore.

The Primary Clinical Research Coordinator (PCRC) or designee will assign the study dose-solution and add the on-study date to complete enrollment.

5.3 Participants Who Do Not Begin the Study

If a participant is registered to the study, and is later found not able to begin the study, for any reason, the participant will be taken off study. The Study Coordinator or designee will update OnCore of the participant's non-study status. The participant will be replaced to fulfill enrollment requirements.

6 Study Plan

6.1 Healthy Volunteers

6.1.1 Dose Assignment

Dose assignments will be defined at the time of study registration using a balanced incomplete block design (Table 1).

	Days 1-3		Days 8	
	(M,T, W – week 1)		(M,T, W –	week 2)
Subject	Solution	Dose	Solution	Dose
1	Α	1	В	2
2	Α	2	В	1
3	В	1	Α	2
4	В	2	Α	1
5	Α	1	В	2
6	Α	2	В	1
7	В	1	Α	2
8	В	2	Α	1
9	Α	1	В	2
10	Α	2	В	1
11	В	1	Α	2
12	В	2	Α	1

The dose levels are 12 and 25 of medical grade oral AC. While the standard AC dose for poison control is 25-100 grams, these smaller doses have been chosen to ensure safety. The AC will be mixed with 4 oz of either tap water or apple juice for a total of 4 combinations.

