10.2 Case Report Forms

Participant data will be collected using protocol specific electronic case report forms (e-CRF) developed within OnCore based on its library of standardized forms. The e-CRF will be approved by the study's Principal Investigator and the Biostatistician prior to release for use. The Primary Clinical Research Coordinator or designee will be responsible for registering the patient into OnCore at time of study entry, completing e-CRF based on the patient specific calendar, and updating the patient record until patient death or end of required study participation.

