12.1 Study Design

This is a pilot study designed to test tolerability and safety of oral AC in 12 healthy volunteers.

We will follow a predetermined treatment assignment using the balanced incomplete block design shown in Section 6.1.1. Twelve healthy subjects will be assigned two dose and solution combinations to take for three days each. Each subject will receive each dose once and each solution once. Different subjects will receive different combinations or different sequences. Each of the four combinations will be given to six subjects total, allowing straightforward comparisons. Each solution (or dose) precedes each of the others for exactly half of the subjects, to minimize confounding due to the ordering of the treatment assignments.

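### Table 1 assigns sequences by a fixed, predictable four-row cycle with no randomisation or concealment, which exposes four of the six comparisons between combinations to selective placement of volunteers

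*Combined protocol and SAP*

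**What the plan says.** Three places describe the allocation, and none mentions a random element.

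- Section 3: "AC solution assignments will be defined before the study using a balanced incomplete block design".
- Section 6.1.1: "Dose assignments will be defined at the time of study registration using a balanced incomplete block design (Table 1".
- Section 12.1: "We will follow a predetermined treatment assignment using the balanced incomplete block design shown in Section 6.1.1".

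Table 1 gives the order A1 then B2, A2 then B1, B1 then A2, B2 then A1, and repeats it three times for subjects 1 to 12 (letter = solution, number = dose level).

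On who does what, section 5.2 says that "the Study Coordinator or designee will enroll the volunteer on study in OnCore", and then: "The Primary Clinical Research Coordinator (PCRC) or designee will assign the study dose-solution and add the on-study date to complete enrollment". Section 10.2 adds: "The Primary Clinical Research Coordinator or designee will be responsible for registering the patient into OnCore at time of study entry". Section 5.3 has non-starters replaced but does not say which row of Table 1 the replacement takes.

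On use of the data, section 12.1 says: "Each of the four combinations will be given to six subjects total, allowing straightforward comparisons". Section 12.3 averages each subject's ratings over the three days of a treatment and chooses the combination with the highest mean. It plans no hypothesis test and no adjustment for subject.

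**The concern.** If row n is known before volunteer n is enrolled, whoever recruits or schedules can influence who fills it, deliberately or not. An example is bringing forward a keen volunteer or holding back a reluctant one. The same applies to choosing a row for a replacement. In a crossover where each volunteer tried every combination, this would matter little, because each person's general rating level would cancel. Here each volunteer tries only two combinations, and Table 1 uses only two pairings. Most comparisons of combinations are therefore comparisons of two different sets of six people. What is at stake is which combinations are carried forward to later trials, the stated purpose of the study.

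**Working it through.** **1. The plan's own counts.** Counting over Table 1, each combination appears in 6 subjects, 3 in week 1 and 3 in week 2. Solution A comes first in 6 of 12 subjects and dose 1 in 6 of 12. This reproduces the six per combination and the order balance claimed in 12.1.

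**2. Which combinations share volunteers.**

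| Group | Subjects | Combinations supplied |
|---|---|---|
| G1 | 1, 4, 5, 8, 9, 12 | A1 and B2 |
| G2 | 2, 3, 6, 7, 10, 11 | A2 and B1 |

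A balanced incomplete block design with v = 4 combinations, k = 2 per subject and r = 6 replicates needs each pair to occur r(k - 1)/(v - 1) = 6 × 1/3 = 2 times. In Table 1 two pairs occur 6 times each and the other four never occur.

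**3. Where a group difference goes.** Let G1 rate g points above G2 for reasons unrelated to product.

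- A1-A2, A1-B1, B2-A2 and B2-B1: bias +g each.
- A1-B2 and A2-B1: bias g - g = 0.
- Solution main effect, (A1 + A2)/2 - (B1 + B2)/2: g/2 - g/2 = 0. The dose main effect cancels in the same way.

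If dose and solution effects are additive, the best combination is always paired in Table 1 with the worst, because the pair differs in both factors. Its two nearest rivals are always in the other group, so g bears on the comparisons that decide the winner.

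**4. Enrolment drift.** Take subject number as enrolment order, which is the natural reading but is not stated.

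- Linear: positions sum to 1 + 4 + 5 + 8 + 9 + 12 = 39 in G1 and 2 + 3 + 6 + 7 + 10 + 11 = 39 in G2. The mean position is 39/6 = 6.5 for every combination, so linear drift contributes 0.
- Quadratic, 1 point over the trial: 0.357 - 0.340 = 0.017 point.
- A 1-point step: 0, or at most 1/6 = 0.17 point.

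**5. Effect on picking the winner.** The documents give no SD, correlation or effect size, so these are assumptions: solution and dose effects of 0.5 point each (combination means 1.0, 0.5, 0.5, 0 on a relative scale), and normal subject-level scores with total SD 1 and intra-subject correlation 0.5 (between- and within-subject variances 0.5 each). Simulating the Table 1 layout and choosing the highest raw mean gives:

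| Shift in the best combination's group | Chance of picking the best |
|---|---|
| none | 0.73 |
| 0.17 lower | 0.62 |
| 0.25 lower | 0.56 |
| 0.5 lower | 0.38 |
| 0.5 higher | 0.93 |

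**6. How large a shift could steering produce?** Suppose that for every slot the enroller chooses between two waiting volunteers to suit the known row. Let the guess correlate ρ with the volunteer's true rating level, and let the between-subject SD be σ. The expected group difference is 2ρσ/√π.

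- σ = 0.5: 0.17 (ρ = 0.3) to about 0.56 (ρ = 1).
- σ = 1.0: 0.34 (ρ = 0.3) to 1.13 (ρ = 1).

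These are upper-end figures, because they assume a choice and a consistent aim at every slot. If the row could not be foreseen, the expected difference would be 0.

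**7. What chance alone does.** With between-subject variance 0.5, the SD of the difference between two randomly formed groups of six is √(0.5 × (1/6 + 1/6)) = 0.41 point.

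**The case against.** **Drift.** A reader might infer that any trend over enrolment also passes into the comparison. It does not. The cycle cancels linear drift exactly and leaves little of other forms (step 4). On this count Table 1 does better than an unrestricted shuffle, whose imbalance has SD 0.19 per point of drift. This objection stands, and it is why the fix below uses blocks of four.

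**Same person enrolling and assigning.** Section 5.2 names two roles, the Study Coordinator for enrolment and the PCRC for assignment. Only 10.2 has the PCRC registering volunteers, and each role may be delegated. One person doing both is possible but not established. The point does not depend on it, because the table is in the protocol and nothing withholds it from anyone.

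**Steering is hypothetical.** Volunteers answer posters, and nothing suggests that staff can foresee who will like charcoal or that they favour a combination. Assignment already follows consent and eligibility confirmation. This limits the weight of the point but does not remove the exposure.

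**Randomising does not remove the underlying weakness.** Chance differences of SD 0.41 would remain under the assumptions above. They come from having two disconnected pairings and comparing raw means. This is correct: random allocation removes systematic selection, not chance imbalance.

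**Scale.** This is a 12-person pilot with no hypothesis test, and it openly states a predetermined assignment. That is fair, but the study still makes a selection, and the safeguard is almost free.

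**Conclusion.** The point holds in limited form. Allocation is predictable and unconcealed, and the two groups of six share no combination. Selective placement would therefore bias four of the six pairwise comparisons one-for-one, and the raw-average rule would not remove it. A1-B2, A2-B1 and both main effects are protected by the design.

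The fall from 0.73 to 0.38 should not be read as a forecast. It is one direction and one size of an assumed shift; the same shift the other way gives 0.93. The documents supply neither the variances nor any evidence that a shift of that size would occur. Nor do they show that steering is likely, or that the dose and solution effects are compromised. The conclusion rests on the structure of Table 1 and the rule in 12.3, and on reading subject number as enrolment order. It supports a cheap improvement and does not invalidate the design.

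**What to change.** - Before enrolment, the biostatistician randomly permutes the four sequences within each block of four subject numbers (24 × 24 × 24 = 13,824 possible lists).
- The list is withheld from all staff who recruit, enrol or schedule. Each row is released only after registration in OnCore.
- A replacement takes the row of the non-starter replaced.
- State this in 5.2, 5.3, 6.1.1 and 12.1. State that subject number follows registration order, and make 5.2 and 10.2 agree on who registers.
- Reconcile section 3, which defines assignments before the study, with 6.1.1, which defines them at registration. A list fixed beforehand and released row by row would satisfy both.

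**Cost.** One random list and a few sentences, with no extra volunteers, visits or staff. Six subjects per combination and three per week are kept.

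**Downsides.**

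- Balance against linear drift becomes slightly less exact: SD about 0.07 per point of drift instead of 0.
- The later rows of a block stay partly guessable to staff who know the block size and the rows already used. They could guess the exact sequence in (1/4 + 1/3 + 1/2 + 1)/4 = 52% of cases, against 100% now. For the group alone, which is what drives the bias, the figure is (1/2 + 2/3 + 2/3 + 1)/4 = 71%. Determined steering could then keep 2 × 0.71 - 1, or about 0.42, of the bias in step 6.
- Chance differences between the two groups of six remain. Reducing those needs all six pairs in the layout or a subject-adjusted analysis, which is a separate change.
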